4.2.1.2 Dose Modification

Adverse events (both non-serious and serious) associated with Pembrolizumab exposure may represent an immunologic etiology. These adverse events may occur shortly after the first dose or several months after the last dose of treatment. Adverse experiences will be graded and recorded throughout the study and during the follow-up period according to NCI CTCAE Version 4.0. Pembrolizumab must be withheld for drug-related toxicities and severe or life-threatening drug-related AEs as per Table 3 below. See Section 4.6.1 and Events of Clinical Interest Guidance Document for supportive care guidelines, including use of corticosteroids.

**Table 3
Dose Modification Guidelines for Drug-Related Adverse Events**

| Toxicity | Hold Treatment For Grade | Timing for Restarting Treatment | Discontinue Subject |
|----------------------------------|--------------------------|---------------------------------|--|
| Diarrhea/Colitis | 2-3 | Toxicity resolves to Grade 0-1. | Toxicity does not resolve within 12 weeks of last dose or inability to reduce corticosteroid to 10 mg or less of prednisone or equivalent per day within 12 weeks. |
| | 4 | Permanently discontinue | Permanently discontinue |
| AST, ALT, or Increased Bilirubin | 2 | Toxicity resolves to Grade 0-1 | Toxicity does not resolve within 12 weeks of last dose. |

| Toxicity | Hold Treatment For Grade | Timing for Restarting Treatment | Discontinue Subject |
|---|--------------------------|---|--|
| | 3-4 | Permanently discontinue | Permanently discontinue |
| Type 1 diabetes mellitus (if new onset) or Hyperglycemia | T1DM or 3-4 | Hold Pembrolizumab for new onset Type 1 diabetes mellitus or Grade 3-4 hyperglycemia associated with evidence of beta cell failure. | Resume Pembrolizumab when patients are clinically and metabolically stable. |
| Hypophysitis | 2-3 | Toxicity resolves to Grade 0-1 | Toxicity does not resolve within 12 weeks of last dose or inability to reduce corticosteroid to 10 mg or less of prednisone or equivalent per day within 12 weeks. |
| | 4 | Permanently discontinue | Permanently discontinue |
| Hyperthyroidism | 3 | Toxicity resolves to Grade 0-1 | Toxicity does not resolve within 12 weeks of last dose or inability to reduce corticosteroid to 10 mg or less of prednisone or equivalent per day within 12 weeks. |
| | 4 | Permanently discontinue | Permanently discontinue |

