4.8 Subject Withdrawal/Discontinuation Criteria

Subjects may withdraw consent at any time for any reason or be dropped from the trial at the discretion of the investigator should any untoward effect occur. In addition, a subject may be withdrawn by the treating sub-investigator or the Principal Investigator if enrollment into the trial is inappropriate, the trial plan is violated, or for administrative and/or other safety reasons. Specific details regarding discontinuation or withdrawal are provided in Section 6.1.4 – Other Procedures.

A subject must be discontinued from the trial for any of the following reasons:

- The subject or legal representative (such as a parent or legal guardian) withdraws consent.
- Confirmed pathologic disease progression
- Unacceptable adverse experiences as described in Section 6.2.1.2
- Intercurrent illness that prevents further administration of treatment
- Investigator's decision to withdraw the subject
- The subject has a confirmed positive serum pregnancy test

- Noncompliance with trial treatment or procedure requirements
- The subject is lost to follow-up
- Completed 24 months of treatment with pembrolizumab and required follow-up
- Administrative reasons

The End of Treatment and Follow-up visit procedures are listed in Section 5 (Trial Flow Chart) and Section 6.1.5 (Visit Requirements). After the end of treatment, each subject will be followed for 30 days for adverse event monitoring (serious adverse events will be collected for 90 days after the end of treatment as described in Section 6.2.3.1). Subjects who discontinue for reasons other than progressive disease will have post-treatment follow-up for disease status until disease progression, initiating a non-study cancer treatment, withdrawing consent or becoming lost to follow-up. After documented disease progression each subject will be followed by telephone for overall survival until death, withdrawal of consent, or the end of the study, whichever occurs first.

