5.0 TRIAL FLOW CHART

5.1 Study Flow Chart

| Trial Period: | Treatment Cycles ^a | | | | | | | | | End of Treatment | Post-Treatment | | | |
|---|-------------------------------|----------------------|-----|-----|-----|-----|--------------------------------|-----|-----|------------------|-------------------|---------------------|-------------------------------|--------------------|
| | Treatment Cycle/Title: | Main Study Screening | 1 | 2 | 3 | 4 | To be repeated beyond 8 cycles | | | | Discon | Safety Follow-up | Follow Up Visits ^b | Survival Follow-Up |
| 5 | | | | | | | 6 | 7 | 8 | | | | | |
| Scheduling Window (Days): | -28 to -1 | | ± 3 | ± 3 | ± 3 | ± 3 | ± 3 | ± 3 | ± 3 | ± 3 | At time of Discon | 30 days post discon | Every 12 weeks post discon | Every 12 weeks |
| Pre-screening Consent | | | | | | | | | | | | | | |
| Informed Consent | X | | | | | | | | | | | | | |
| Inclusion/Exclusion Criteria | X | | | | | | | | | | | | | |
| Subject Identification Card | | X | X | X | X | X | X | X | X | X | X | X | X | |
| Demographics and Medical History | X | | | | | | | | | | | | | |
| Prior and Concomitant Medication Review | X | X | X | X | X | X | X | X | X | X | | | | |
| Trial Treatment Administration | | X | X | X | X | X | X | X | X | X | | | | |
| Post-study anticancer therapy status | | | | | | | | | | | | | X | X |
| Survival Status | | | | | | | | | | | | | | X |
| Review Adverse Events | | X | X | X | X | X | X | X | X | X | X | X | | |
| Full Physical Examination | X | | | | X | | | | | X | X | X | | |
| Directed Physical Examination | | X | X | X | | X | X | X | | | | | | |
| Vital Signs and Weight | X | X | X | X | X | X | X | X | X | X | X | X | | |
| ECOG Performance Status | X | X | X | X | | X | | X | | X | X | | | |
| Pregnancy Test – Urine or Serum β-HCG | X | X ^c | | | | | | | | | | | | |
| PT/INR and aPTT | X | | | | | | | | | | | | | |
| CBC with Differential | X ^d | X | X | X | X | X | X | X | X | X | X | X | X | |
| Comprehensive Serum Chemistry Panel | X ^d | X | X | X | X | X | X | X | X | X | X | X | | |
| Urinalysis | X ^d | | X | | X | | X | | X | X | X | | | |

| Trial Period: | Treatment Cycles ^a | | | | | | | | | End of Treatment | Post-Treatment | | |
|---|-------------------------------|---|-----|-----|-----|--------------------------------|-----|-----|----------------|-------------------|---------------------|-------------------------------|--------------------|

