6.1.5.4 Follow-up Visits

Subjects who discontinue trial treatment for a reason other than disease progression will move into the Follow-Up Phase and should be assessed every 12 weeks (84 ± 7 days) by complete blood count to monitor disease status. Every effort should be made to collect information regarding disease status until the start of new anti-neoplastic therapy, disease progression, death, or end of the study or up to 5 years from enrollment. Information regarding post-study anti-neoplastic treatment will be collected if new treatment is initiated.

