6.1.5.4.1 Survival Follow-up

Once a subject experiences confirmed disease progression or starts a new anti-cancer therapy, the subject moves into the survival follow-up phase and should be contacted by telephone every 12 weeks to assess for survival status until death, withdrawal of consent, or the end of the study, whichever occurs first.

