6.2 Assessing and Recording Adverse Events

An adverse event is defined as any untoward medical occurrence in a patient or clinical investigation subject administered a pharmaceutical product and which does not necessarily have to have a causal relationship with this treatment. An adverse event can therefore be any unfavorable and unintended sign (including an abnormal laboratory finding, for example), symptom, or disease temporally associated with the use of a medicinal product or protocol-specified procedure, whether or not considered related to the medicinal product or protocol-specified procedure. Any worsening (i.e., any clinically significant adverse change in frequency and/or intensity) of a preexisting condition that is temporally associated with the use of the investigational product, is also an adverse event.

Changes resulting from normal growth and development that do not vary significantly in frequency or severity from expected levels are not to be considered adverse events. Examples of this may include, but are not limited to, teething, typical crying in infants and children and onset of menses or menopause occurring at a physiologically appropriate time.

Adverse events may occur during the course of the use of the investigational product in clinical trials or within the follow-up period specified by the protocol, or prescribed in clinical practice, from overdose (whether accidental or intentional), from abuse and from withdrawal.

Adverse events may also occur in screened subjects during any pre-allocation baseline period as a result of a protocol-specified intervention, including washout or discontinuation of usual therapy, diet, placebo treatment or a procedure.

All adverse events will be recorded from the time the consent form is signed through 30 days following cessation of treatment and at each examination on the Adverse Event case report forms/worksheets. The reporting timeframe for adverse events meeting any serious criteria is described in section 6.2.3.1.

Adverse events will not be collected for subjects during the pre-screening period (for determination of archival tissue status) as long as that subject has not undergone any protocol-specified procedure or intervention. If the subject requires a blood draw, fresh tumor biopsy etc., the subject is first required to provide consent to the main study and AEs will be captured according to guidelines for standard AE reporting.

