6.2.3 Immediate Reporting of Adverse Events to the Investigator and to Merck

6.2.3.1 Serious Adverse Events

A serious adverse event is any adverse event occurring at any dose or during any use of the investigational product that:

- Results in death;
- Is life threatening;
- Results in persistent or significant disability/incapacity;
- Results in or prolongs an existing inpatient hospitalization;
- Is a congenital anomaly/birth defect;
- Is a new cancer (that is not a condition of the study);
- Is associated with an overdose;
- Is another important medical event

Progression of the cancer under study is not considered an adverse event unless it results in hospitalization or death.

Any serious adverse event, or follow up to a serious adverse event, including death due to any cause other than progression of the cancer under study that occurs to any subject from the time the consent is signed through 90 days following cessation of treatment, or the initiation of new anti-cancer therapy, whichever is earlier, whether or not related to the investigational product, must be reported within 24 hours to the Investigator and within 2 working days to Merck Global Safety.

Non-serious Events of Clinical Interest will be forwarded to Merck Global Safety and will be handled in the same manner as SAEs.

Additionally, any serious adverse event, considered by an investigator who is a qualified physician to be related to the investigational product that is brought to the attention of the investigator at any time outside of the time period specified in the previous paragraph also must be reported immediately to the Investigator and to Merck.

SAE reports and any other relevant safety information are to be forwarded to the Merck Global Safety [contact]

All subjects with serious adverse events must be followed up for outcome.

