6.2.3.2 Events of Clinical Interest

Selected non-serious and serious adverse events are also known as Events of Clinical Interest (ECI) and must be recorded as such on the Adverse Event case report forms/worksheets and reported within 24 hours to the Investigator and within 2 working days to Merck Global Safety. (Attn: Worldwide Product Safety; [contact])

Events of clinical interest for this trial include:

1. an overdose of the investigational product, as defined in Section 6.2.1 - Definition of an Overdose for This Protocol and Reporting of Overdose to the Investigator, that is not associated with clinical symptoms or abnormal laboratory results.
2. an elevated AST or ALT lab value that is greater than or equal to 3X the upper limit of normal and an elevated total bilirubin lab value that is greater than or equal to 2X the upper limit of normal and, at the same time, an alkaline phosphatase lab value that is less than 2X the upper limit of normal, as determined by way of protocol-specified laboratory testing or unscheduled laboratory testing.*

*Note: These criteria are based upon available regulatory guidance documents. The purpose of the criteria is to specify a threshold of abnormal hepatic tests that may require an additional evaluation for an underlying etiology. The trial site guidance for assessment and follow up of these criteria can be found in the Investigator Trial File Binder (or equivalent).

1. Additional adverse events:

A separate guidance document has been provided entitled “Event of Clinical Interest Guidance Document” (previously entitled, “Event of Clinical Interest and Immune-Related Adverse Event Guidance Document”).

ECIs (both non-serious and serious adverse events) identified in this guidance document from the date of first dose through 90 days following cessation of treatment, or 30 days after the initiation of a new anticancer therapy, whichever is earlier, need to be reported within 24 hours to the Investigator and within 2 working days to Merck Global Safety. (Attn: Worldwide Product Safety; [contact]), regardless of attribution to study treatment, consistent with standard SAE reporting guidelines.

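### SAEs and ECIs are reportable to day 90 after treatment, but scheduled adverse-event review stops at day 30, so capture in days 31 to 90 relies on spontaneous or unscheduled reports

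*Combined protocol and SAP*

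**What the plan says.** **Late onset.** On adverse events of possible immunologic origin, section 4.2.1.2 says: "These adverse events may occur shortly after the first dose or several months after the last dose of treatment".

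**Reporting windows.**
- SAEs (6.2.3.1): from consent "through 90 days following cessation of treatment, or the initiation of new anti-cancer therapy, whichever is earlier". Section 6.1.5.3.1 also asks for SAEs to day 90, or before new therapy, to be followed and recorded.
- ECIs, serious and non-serious (6.2.3.2): "from the date of first dose through 90 days following cessation of treatment, or 30 days after the initiation of a new anticancer therapy" (the earlier applies).
- All adverse events (6.2): "All adverse events will be recorded from the time the consent form is signed through 30 days following cessation of treatment". Section 4.8 agrees: "After the end of treatment, each subject will be followed for 30 days for adverse event monitoring". For SAEs, 4.8 adds a 90-day period and refers to 6.2.3.1.

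**Scheduled assessments.**
- The flow-chart row "Review Adverse Events" is marked through the treatment cycles, at discontinuation and at the 30-day Safety Follow-up. It is blank for the Follow Up Visits and for Survival Follow-Up.
- Section 6.2.3.2 schedules ECI assessment before each dose and at no later time.
- Follow-up visits (6.1.5.4), every 84 ± 7 days, assess patients "by complete blood count to monitor disease status".
- Patients who progress or start new therapy (6.1.5.4.1) "should be contacted by telephone every 12 weeks to assess for survival status".

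**The concern.** The protocol expects immune events after the last dose and sets a 90-day window to collect the important ones. It then schedules questioning for only the first 30 days. A reporting duty without a contact that asks about events depends on the patient volunteering them, on a hospital admission becoming known, or on a test done for another reason.

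Safety is one of the two primary objectives (2.1), and section 7.2.2 tabulates adverse events by type, grade and association with treatment. With 40 patients in one arm, a few uncaptured events would change that table. Unexpected grade 3-4 events also count toward the stopping rule in 7.3, which states no end date, so a late event that nobody elicits would not enter the count either.

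**Working it through.** No sample-size or power figure bears on this point. The check sets the reporting windows against the schedule. Day 0 is the end of treatment, and last dose, cessation and discontinuation are taken as the same day (an assumption, since the sections use different terms).

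**Step 1: flow-chart marks after treatment (5.1).**

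| Row | Discontinuation | Day 30 | 12-weekly visit | Survival call |
|---|---|---|---|---|
| Adverse-event review | X | X | blank | blank |
| Chemistry panel | X | X | blank | blank |
| Thyroid tests | X | X | blank | blank |
| Blood count | X | X | X | blank |
| Post-study therapy status | blank | blank | X | X |
| Survival status | blank | blank | blank | X |

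The chart is wide, so column alignment matters. In its text copy the treatment-administration row has 9 marks, all in cycle columns. The adverse-event row has 11, which is 9 + discontinuation + day 30. The blood-count row has 13, which is screening + 9 + discontinuation + day 30 + the 12-weekly visit. The rows agree with each other and with the prose of 6.1.5.4.

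**Step 2: longest unreviewed stretch.** 90 − 30 = 60 days (days 31 to 90). 60/90 = 67% of the window. This holds for a patient who starts no new therapy by day 90.

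**Step 3: effect of new anti-cancer therapy on day s.** The SAE window closes at min(90, s) and the ECI window at min(90, s + 30). If s is within 30 days of the last dose, sections 6.1.1.5.3 and 6.1.5.3.1 place the safety visit before the new therapy, so review reaches about day s. The values of s below are illustrative.

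| s | Review ends | SAE window ends | SAE days unreviewed | ECI window ends | ECI days unreviewed |
|---|---|---|---|---|---|
| 28 | about 28 | 28 | 0 | 58 | about 30 |
| 45 | 30 | 45 | 15 | 75 | 45 |
| 60 | 30 | 60 | 30 | 90 | 60 |
| none | 30 | 90 | 60 | 90 | 60 |

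Sixty days is therefore a maximum. For SAEs the gap closes in patients who switch early. For ECIs a tail of about 30 days remains even then.

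**Step 4: what the existing contact could cover.** The first 12-week visit falls on day 84 − 7 = 77 to 84 + 7 = 91. If it asked about events since the safety visit, at most 90 − 77 = 13 days would stay uncovered, and none at day 90 or 91. The ± 7 days is stated for clinic follow-up visits; no tolerance is given for survival calls.

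**Step 5: do other sections fill the gap?**
- 6.1.2.1 extends grading and recording into follow-up, but ties assessment to the flow chart, with more only when clinically indicated.
- 6.1.5.3.1 follows events already above Grade 1 to resolution or new therapy and asks for SAEs to day 90 to be recorded. It schedules no contact to find new ones.
- 6.2.3.1 covers related SAEs outside the window, but only those that reach the investigator.
- The hepatic ECI in 6.2.3.2 is defined by laboratory values. With chemistry last scheduled at day 30, a later case can be found only by unscheduled testing.

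Each provides for recording or reporting. None provides a scheduled question.

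**The case against.** A reader might infer that late immune toxicity will be missed or under-counted. The documents do not support that. SAE and ECI reporting to day 90 is mandatory, recording extends into follow-up, and the 12-weekly visit or call is still a contact at which events can surface. No late-event rate is given. The gap is in active elicitation, and its cost in events is unknown.

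Other strong readings also fail or shrink:

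- **That 67% of the window is unreviewed for all 40 patients.** Step 3 shows this to be a maximum.
- **That section 4.8 sets a separate flat 90-day SAE rule.** It defers to 6.2.3.1, which carries the new-therapy limit. The real difference is between SAEs (at the start of therapy) and ECIs (30 days later).
- **That a non-serious ECI on day 45 is both reportable and unrecordable.** Section 6.2.3.1 handles non-serious ECIs like SAEs, and 6.2.3.2 puts them on the adverse-event forms with their own window. That specific rule largely settles the matter against the general 30-day rule, though 4.8 and 6.2 do not say so.
- **That medications for SAEs and ECIs are recorded only to day 30.** Section 4.5.1 reads that way, but 6.1.1.4.2 requires all medications related to reportable SAEs and ECIs. The two need aligning.
- **That later contacts collect only a blood count or survival status.** Post-study therapy status is marked at both, although it does not elicit adverse events.

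The separate ECI guidance document is not available here and could direct assessment after treatment. That limits certainty about practice but does not change the protocol's own schedule, which 6.1.2.1 makes the reference for adverse-event assessment.

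**Conclusion.** The mismatch between window and schedule stands. Up to 60 of the 90 post-treatment days have no scheduled adverse-event or ECI review, and fewer where new anti-cancer therapy shortens the window. Capture in that period rests on spontaneous or unscheduled reports and may be incomplete. The number of events at risk cannot be estimated from the documents.

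This rests on the flow chart as printed, on a common day 0, and on the ECI guidance document not adding scheduled post-treatment assessments. It does not invalidate the safety analysis. It is a low-cost improvement worth making because safety is a primary objective and the protocol itself expects late immune events.

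**What to change.** - **Flow chart (5.1).** Mark adverse-event review at the first 12-week post-treatment contact, whether clinic visit or survival call. Ask about SAEs, ECIs and related medications since the safety visit. Mirror this in 6.1.5.4 and 6.1.5.4.1; 6.1.2.1 then follows, because it points to the chart.
- **Timing.** The 84 ± 7 day schedule can stay. Aim for the late end, because a day-77 contact leaves up to 13 days uncovered.
- **New-therapy cut-off.** Reconcile 6.2.3.1 with 6.2.3.2, and carry the result into 4.8 and 6.1.5.3.1.
- **ECI window.** State in 4.8 and 6.2 that ECIs follow the 90-day window rather than the general 30-day rule.
- **Medications.** Align the 30-day limit in 4.5.1 with 6.1.1.4.2.

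The cost is protocol wording and a few case-report-form fields at a contact already planned, with no new visit or test. The drawbacks are slightly more adverse-event data, some of it confounded by later therapy, and recall over roughly 47 to 61 days (77 − 30 to 91 − 30). A question will not find a symptomless hepatic ECI, which would still depend on unscheduled chemistry.

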6.2.4 Evaluating Adverse Events

An investigator who is a qualified physician will evaluate all adverse events according to the NCI Common Terminology for Adverse Events (CTCAE), version 4.0. Any adverse event which changes CTCAE grade over the course of a given episode will have each change of grade recorded on the adverse event case report forms/worksheets.

All adverse events regardless of CTCAE grade must also be evaluated for seriousness.

Table 10: Evaluating Adverse Events

An investigator who is a qualified physician, will evaluate all adverse events as to:

| | | | | | | | | |
|----------------------------------|--|---|-----------------|--|--------------------|---|---------------------|---|
| V4.0 CTCAE Grading | Grade 1 | Mild; asymptomatic or mild symptoms; clinical or diagnostic observations only; intervention not indicated. | | | | | | |
| | Grade 2 | Moderate; minimal, local or noninvasive intervention indicated; limiting age-appropriate instrumental ADL. | | | | | | |
| | Grade 3 | Severe or medically significant but not immediately life-threatening; hospitalization or prolongation or hospitalization indicated; disabling; limiting self-care ADL. | | | | | | |
| | Grade 4 | Life threatening consequences; urgent intervention indicated. | | | | | | |
| | Grade 5 | Death related to AE | | | | | | |
| Seriousness | 
A serious adverse event is any adverse event occurring at any dose or during any use of investigational product that:
 
†Results in death; or
 
†Is life threatening; or places the subject, in the view of the investigator, at immediate risk of death from the event as it occurred (Note: This does not include an adverse event that, had it occurred in a more severe form, might have caused death.); or
 
†Results in a persistent or significant disability/incapacity (substantial disruption of one’s ability to conduct normal life functions); or
 
†Results in or prolongs an existing inpatient hospitalization (hospitalization is defined as an inpatient admission, regardless of length of stay, even if the hospitalization is a precautionary measure for continued observation. (Note: Hospitalization [including hospitalization for an elective procedure] for a preexisting condition which has not worsened does not constitute a serious adverse event.); or
 
†Is a congenital anomaly/birth defect (in offspring of subject taking the product regardless of time to diagnosis); or
 
Is a new cancer; (that is not a condition of the study) or
 
Is an overdose (whether accidental or intentional). Any adverse event associated with an overdose is considered a serious adverse event. An overdose that is not associated with an adverse event is considered a non-serious event of clinical interest and must be reported within 24 hours.
 
Other important medical events that may not result in death, not be life threatening, or not require hospitalization may be considered a serious adverse event when, based upon appropriate medical judgment, the event may jeopardize the subject and may require medical or surgical intervention to prevent one of the outcomes listed previously (designated above by a †).
 | | | | | | | |
| Duration | Record the start and stop dates of the adverse event. If less than 1 day, indicate the appropriate length of time and units | | | | | | | |
| Action taken | Did the adverse event cause the investigational product to be discontinued? | | | | | | | |
| Relationship to test drug | 
Did the investigational product cause the adverse event? The determination of the likelihood that the investigational product caused the adverse event will be provided by an investigator who is a qualified physician. The investigator’s signed/dated initials on the source document or worksheet that supports the causality noted on the AE form, ensures that a medically qualified assessment of causality was done. This initialed document must be retained for the required regulatory time frame. The criteria below are intended as reference guidelines to assist the investigator in assessing the likelihood of a relationship between the test drug and the adverse event based upon the available information.
 
The following components are to be used to assess the relationship between the investigational product and the AE; the greater the correlation with the components and their respective elements (in number and/or intensity), the more likely the investigational product caused the adverse event (AE):
 
 
 Exposure	Is there evidence that the subject was actually exposed to the investigational product such as: reliable history, acceptable compliance assessment (pill count, diary, etc.), expected pharmacologic effect, or measurement of drug/metabolite in bodily specimen?	
 
 Time Course	Did the AE follow in a reasonable temporal sequence from administration of the investigational product? Is the time of onset of the AE compatible with a drug-induced effect (applies to trials with investigational medicinal product)?	
 
 Likely Cause	Is the AE not reasonably explained by another etiology such as underlying disease, other drug(s)/vaccine(s), or other host or environmental factors	
 
 | | Exposure | Is there evidence that the subject was actually exposed to the investigational product such as: reliable history, acceptable compliance assessment (pill count, diary, etc.), expected pharmacologic effect, or measurement of drug/metabolite in bodily specimen? | Time Course | Did the AE follow in a reasonable temporal sequence from administration of the investigational product? Is the time of onset of the AE compatible with a drug-induced effect (applies to trials with investigational medicinal product)? | Likely Cause | Is the AE not reasonably explained by another etiology such as underlying disease, other drug(s)/vaccine(s), or other host or environmental factors |
| Exposure | Is there evidence that the subject was actually exposed to the investigational product such as: reliable history, acceptable compliance assessment (pill count, diary, etc.), expected pharmacologic effect, or measurement of drug/metabolite in bodily specimen? | | | | | | | |
| Time Course | Did the AE follow in a reasonable temporal sequence from administration of the investigational product? Is the time of onset of the AE compatible with a drug-induced effect (applies to trials with investigational medicinal product)? | | | | | | | |
| Likely Cause | Is the AE not reasonably explained by another etiology such as underlying disease, other drug(s)/vaccine(s), or other host or environmental factors | | | | | | | |

| | | |
|--|--|---|
| Relationship to investigational product (continued) | The following components are to be used to assess the relationship between the test drug and the AE: (continued) | |
| | Dechallenge | Was the investigational product discontinued or dose/exposure/frequency reduced? If yes, did the AE resolve or improve? If yes, this is a positive dechallenge. If no, this is a negative dechallenge. (Note: This criterion is not applicable if: (1) the AE resulted in death or permanent disability; (2) the AE resolved/improved despite continuation of the investigational product; or (3) the trial is a single-dose drug trial; or (4) investigational product(s) is/are only used one time.) |
| | Rechallenge | Was the subject re-exposed to the investigational product in this study? If yes, did the AE recur or worsen? If yes, this is a positive rechallenge. If no, this is a negative rechallenge. (Note: This criterion is not applicable if: (1) the initial AE resulted in death or permanent disability, or (2) the trial is a single-dose drug trial); or (3) investigational product(s) is/are used only one time). NOTE: IF A RECHALLENGE IS PLANNED FOR AN ADVERSE EVENT WHICH WAS SERIOUS AND WHICH MAY HAVE BEEN CAUSED BY THE MERCK PRODUCT, OR IF REEXPOSURE TO THE INVESTIGATIONAL PRODUCT POSES ADDITIONAL POTENTIAL SIGNIFICANT RISK TO THE SUBJECT, THEN THE RECHALLENGE MUST BE APPROVED IN ADVANCE BY THE U.S. CLINICAL MONITOR AS PER DOSE MODIFICATION GUIDELINES IN THE PROTOCOL. |
| | Consistency with Trial Treatment Profile | Is the clinical/pathological presentation of the AE consistent with previous knowledge regarding the investigational product or drug class pharmacology or toxicology? |
| The assessment of relationship will be reported on the case report forms /worksheets by an investigator who is a qualified physician according to his/her best clinical judgment, including consideration of the above elements. | | |
| Record one of the following | Use the following scale of criteria as guidance (not all criteria must be present to be indicative of a investigational product relationship). | |
| Yes, there is a reasonable possibility of Merck product relationship. | There is evidence of exposure to the investigational product. The temporal sequence of the AE onset relative to the administration of the investigational product is reasonable. The AE is more likely explained by the investigational product than by another cause. | |
| No, there is not a reasonable possibility Merck product relationship | Subject did not receive the investigational product OR temporal sequence of the AE onset relative to administration of the investigational product is not reasonable OR there is another obvious cause of the AE. (Also entered for a subject with overdose without an associated AE.) | |

